**Safety**

The safety endpoints of the study are the incidence of treatment-emergent AEs (TEAEs), clinical laboratory assessments, vital signs (blood pressure, pulse rate, respiration rate, and temperature), physical and neurological examination assessments, prior and concomitant medications.

**Pharmacokinetic**

Trough concentrations (Ctrough) of cannabidiol (CBD) and metabolite 7-hydroxy-CBD (7-OH-CBD) will be used to assess the exposure-response relationship.

## **Statistical methods:**

### **Sample Size Calculation**

A total of 180 patients (120 and 60 patients in the two groups) will provide 80% power with a two-sided alpha of 0.05 to detect a difference in response rate, assuming the response with vigabatrin alone is 40% and the response with vigabatrin with Cannabidiol Oral Solution is 62%.

### **Analysis Populations**

Statistical analyses will be conducted on the following populations:

- Safety Population: The Safety Population will include all patients who were treated with at least one dose of the study drug.
- Intent to Treat (ITT) Population: The ITT Population will include all patients who were randomized.

### **Efficacy Analyses**

The ITT Population will be used for all efficacy analyses.

- For the primary endpoint, a 2-sided Type I error rate of 0.05 will be used.
- For the secondary efficacy endpoints, to maintain the trial-wise Type I error rate at 0.05, False Discovery Rate multiple comparisons correction will be used.
- For endpoints that are continuous in nature, the number of observations, mean, median, minimum and maximum, and standard deviation (SD) values will be presented as descriptive statistics. For inferential statistics, a t-test or ANCOVA will be used to compare treatment to placebo group.
- For endpoints that are categorical in nature, frequency, counts, and percentages will be presented as descriptive statistics, and Fisher's exact test, Cochran-Maentel-Haenzel, or logit model will be used for inferential statistics as appropriate.

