- Investigator impression of efficacy and tolerability of study drug (CGI-I) at Visit 6 (End of Study) or Early Withdrawal.
- Increase in the number of spasm-free days between Day 1 and Day 15 of the Initial Treatment Period, as determined by the seizure diary entries.
- For patients with a complete response during the Initial Treatment Period who continue: percent of patients who relapse during the Extended Treatment Period confirmed by video EEG following parent report of relapse, and time to relapse.

Safety

The safety endpoints of the study are the incidence of treatment-emergent AEs (TEAEs), clinical laboratory assessments, vital signs (blood pressure, pulse rate, respiration rate, and temperature), physical and neurological examination assessments, prior and concomitant medications, liver enzymes and serum bilirubin.

Pharmacokinetics

Trough concentrations (C_{trough}) of cannabidiol (CBD) and 7-OH-CBD will be used to assess the exposure-response relationship. A meal diary will be used to record the type of meals consumed in relation to the PK blood draws.

Statistical methods:**Sample Size Calculation**

A total of 190 patients (130 and 60 patients in the two groups) will provide 80% power with a two-sided alpha of 0.05 to detect a difference in response rate, assuming the response with vigabatrin alone is 40% and the response with vigabatrin with Cannabidiol Oral Solution is 60%.

Analysis Populations

Statistical analyses will be conducted on the following populations:

- Safety Population: The Safety Population will include all patients who were treated with at least one dose of the study drug.
- Intent to Treat (ITT) Population: The ITT Population will include all patients who were randomized.
- PK Population: The PK Population will include all patients who were treated with at least one dose of the study drug and have at least one usable PK measurement.

Efficacy Analyses

The ITT Population will be used for all efficacy analyses in the Initial Treatment Period.

- For the primary endpoint, a 2-sided Type I error rate of 0.05 will be used.
- For the secondary efficacy endpoints, to maintain the trial-wise Type I error rate at 0.05, a fixed sequence multiple comparisons correction with fallback will be used. The assignment of alpha levels to hypotheses being tested will be specified in the Statistical Analysis Plan.

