- For endpoints that are continuous in nature, the number of observations, mean, median, minimum and maximum, and standard deviation (SD) values will be presented as descriptive statistics. For inferential statistics, a t-test will be used to compare treatment to placebo group.
- For endpoints that are categorical in nature, frequency, counts, and percentages will be presented as descriptive statistics, and a chi-square test will be used for inferential statistics.

Primary Efficacy Analysis

- Percent of patients with complete resolution of both infantile spasms and hypsarrhythmia at Day 15 (complete response) will be compared between vigabatrin plus placebo and vigabatrin plus CBD 40 mg/kg/day groups using a chi-square test.

Secondary Efficacy Analyses

- Percent of patients who relapse during the Extended Treatment Period will be compared between 14-day complete responders receiving vigabatrin + CBD and complete responders receiving 14-day vigabatrin + placebo using chi-square test. Time to relapse will be described with Kaplan-Meier curves and treatment groups compared using a log-rank test.

- Percent of patients with complete resolution of infantile spasms at Day 15 will be compared between treatment groups using a chi-square test.
- Percent of patients with complete resolution of hypsarrhythmia at Day 15 will be compared between treatment groups using a chi-square test.
- Investigator impression of efficacy and tolerability of study drug (Clinical Global Impression – Global Improvement [CGI-I]) will be compared between treatment groups using ANCOVA with baseline CGI-S as a covariate.
- Reduction in percentage of spasm-free days between the Initial Treatment Period and Screening Period will be compared between treatment groups using ANCOVA with the Screening Period percent spasm-free days as a covariate.

Secondary Efficacy Analyses for patients with a complete response during the Initial Treatment Period who continue to the Extended Treatment Period:

- Percent of patients who relapse during the Extended Treatment Period confirmed by video-EEG following parent report of relapse.
- Time to relapse.

Safety Analyses

The Safety Population will be used for all safety assessments. All safety assessments will be descriptive and no inferential statistics are planned for safety assessments. All data listings will be provided for protocol specified safety data.

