8.1.2. Secondary Efficacy Endpoints

The secondary efficacy endpoints in the Initial Treatment Period of this study are:

- Percent of patients with resolution of infantile spasms as assessed by 24-hour video EEG from Day 14 to Day 15 (partial response).
- Percent of patients with resolution of hypsarrhythmia as assessed by 24-hour video EEG from Day 14 to Day 15 (partial response).
- Investigator impression of efficacy and tolerability of study drug (CGI-I) at Visit 6 (End of Study), or Early Withdrawal.
- Increase in the number of spasm-free days between Day 1 and Day 15 of the Initial Treatment Period, as determined by the seizure diary entries.
- For patients with a complete response during the Initial Treatment Period who continue: percent of patients who relapse during the Extended Treatment Period confirmed by video EEG following parent report of relapse, and time to relapse.

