8.4.3. Efficacy Analyses

A 9-hour video EEG will be conducted during the Screening Period (Baseline) and a 24-hour video EEG will be conducted from Day 14 to Day 15 of the Initial Treatment Period. In addition, to confirm parent/caregiver report of relapse or complete resolution a 9-hour video EEG will be conducted during the Extended Treatment Period. For each video EEG, the number of spasms will be counted and the presence of hypsarrhythmia determined. Change from Baseline for each measure will be summarized by the median difference. Patients will be defined as having Complete Response, Partial Response, or Non-Response on Day 15 as defined in [Table 2](#), the percentage of patients who achieve a Complete Response and Partial Responders in each treatment arm will be compared using a chi-square test.

The results of the CGI-I assessments will be listed and summarized by descriptive statistics as appropriate. The responses to the seizure diary will also be summarized by dose level and scheduled time point. All efficacy summaries will be based on the ITT Population.

Details of these summaries will be provided in the SAP. For all inferential statistical tests, a 2-sided type I error rate of 0.05 will be used throughout.

For the secondary efficacy endpoints, to maintain the trial-wise type I error rate at 0.05, a fixed sequence multiple comparisons correction with fallback will be used. The assignment of alpha levels to hypotheses being tested will be specified in the SAP.

For endpoints that are continuous in nature number, the number of observations, mean, median, minimum and maximum, and standard deviation (SD) values will be presented as descriptive statistics. For inferential statistics:

- If the normality assumption is met, analysis of covariance (ANCOVA) using the baseline value as a covariate will be used.
- If the normality assumption is not met, a rank-ANCOVA analysis i.e., an ANCOVA analysis on rank-transformed data or other non-parametric methods will be used.
- Time to event analyses will be described with Kaplan-Meier curves and treatment groups compared with log-rank tests.

For endpoints that are categorical in nature, frequency, counts, and percentages will be presented as descriptive statistics, and a chi-square test will be used for inferential statistics.

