#### **10.5. Multiple Comparisons and Multiplicity**

No multiple comparisons are planned for analysis of the Primary Efficacy Endpoint. Secondary Endpoints will have an FDR correction applied to control the overall  $q = 0.05$ .

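### The SAP's False Discovery Rate correction does not maintain the trial-wise Type I error at 0.05 as it claims, and the fixed-sequence-with-fallback levels that the protocol leaves to the SAP are not there

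*SAP*

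**What the plan says.** **SAP.** The synopsis (Efficacy Analyses) says: "For the secondary efficacy endpoints, to maintain the trial-wise Type I error rate at 0.05, False Discovery Rate multiple comparisons correction will be used". Section 10.5 says: "Secondary Endpoints will have an FDR correction applied to control the overall" q = 0.05, and that no multiple comparisons are planned for the primary. Neither place names an FDR procedure. Section 10.3.2 states eight secondary hypotheses:
- spasm resolution
- hypsarrhythmia resolution
- CGI-I
- spasm-free days
- relapse rate
- time to relapse
- rate of partial-to-complete response
- time to complete response

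**Protocol.** The synopsis (Efficacy Analyses) and Section 8.4.3 say that, to hold the same trial-wise 0.05, "a fixed sequence multiple comparisons correction with fallback will be used". Section 8.4.3 adds: "The assignment of alpha levels to hypotheses being tested will be specified in the SAP". The synopsis also says: "For the primary endpoint, a 2-sided Type I error rate of 0.05 will be used", and Section 8.4.3 says: "For all inferential statistical tests, a 2-sided type I error rate of 0.05 will be used throughout".

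**Not stated in either document.** There is no testing order, no weights, no carry-forward rule, and no statement that the secondaries are tested only after a significant primary.

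**The concern.** The SAP synopsis claims an error rate that its method does not control. FDR control limits the expected proportion of false claims among the claims made. It limits the chance of any false claim to the same level only when every null in the family is true. If some secondary effects are real, those rejections relax the thresholds for the remaining tests.

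The two documents also prescribe different decision rules for the same endpoints, and the protocol's rule cannot be run until the SAP supplies what was left to it. If this is settled after unblinding, the choice of method, order and weights could depend on the data.

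At stake are the secondary claims. They could be presented as controlled at a trial-wise 0.05 when they are not, and nothing written prevents them from being made after a failed primary.

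**Working it through.** **Inputs from the documents.** Target rate 0.05; q = 0.05; eight secondary hypotheses (SAP 10.3.2); primary at two-sided 0.05; SAP design of 120 and 60 patients with response rates of 62% and 40%.

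**Assumptions.** Benjamini-Hochberg as the FDR procedure; two-sided z-tests; equal correlation between endpoints from 0 to 0.7; 400,000 replicates. The documents give none of these.

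**Step 1. Size of a design effect.** Pooled response = (0.40×60 + 0.62×120)/180 = 0.547. The z-shift is 0.22/√[0.547×0.453×(1/60 + 1/120)] = 0.22/0.0787 ≈ 2.8. A shift of 2.6 was run as well.

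**Step 2. Where the SAP's 0.05 is reproduced.** Benjamini-Hochberg rejects the k smallest p-values, where k is the largest value with p(k) ≤ 0.05·k/m. With all eight secondary nulls true, the chance of any false rejection is 0.050 at correlation 0 and 0.043 at 0.5. In that configuration the claim holds for the secondary family.

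**Step 3. Where it is not reproduced.** Four of the eight nulls true, the other four effects real:

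| z-shift of the real effects | corr. 0 | 0.3 | 0.5 | 0.7 |
|---|---|---|---|---|
| 2.6 | 8.6% | 7.7% | 6.7% | 5.5% |
| 2.8 | 9.3% | 8.3% | 7.0% | 5.5% |

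The upper end can be checked by hand. If four effects are so large that they are always rejected, the smallest of the four null p-values is compared with 0.05×5/8 = 0.03125. With independent tests, the chance that at least one null falls below this is 1 − (1 − 0.03125)^4 = 0.119. Simulation at a shift of 6 gives 0.120.

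**Step 4. Where it is not exceeded.** With one null among the eight and shifts of 2.6-2.8, the rate is 2.9-4.1%; with very large effects it is 5.0%.

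**Step 5. The protocol's method.** Under fallback, hypothesis i is tested at its own weight, plus the level carried over from the preceding hypothesis if that one was rejected. The weights sum to 0.05. With equal weights (assumed), the simulated secondary-family error was 0.040-0.050 in every configuration of six or eight tests.

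**Step 6. The missing gate, taken separately.** Suppose all nulls are true, the primary is tested at 0.05 and the secondaries are tested regardless. For a primary independent of a secondary family held at 0.05, the rate is 1 − 0.95² = 0.0975. Over correlations 0 to 0.7, simulation gives 7.0-9.8% with Benjamini-Hochberg and 6.7-9.7% with fallback. With a gate, fallback gives 0.049-0.050. The reason is direct: if the primary null is true, any false claim first needs a false primary rejection (at most 0.05); if it is false, fallback limits the secondaries to 0.05.

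**The case against.** **The inflation is modest and depends on assumptions.** This stands. A patient-level simulation closer to the SAP (Fisher's exact test, 120 and 60 patients, the four Day-14 secondaries only, two of them null) gives 4.3-5.9%. The 12% needs effects far above the design size. What does not depend on these inputs is that FDR offers no guarantee of 0.05.

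**The SAP is tied to an earlier protocol.** SAP Section 1 names the version of 30 October 2017, allows updates for amendments and requires finalisation before database lock. This probably explains the conflict with the protocol, and it means the gap can still be closed. It does not excuse the synopsis sentence, which misdescribes FDR under any protocol version. Section 10.5, read alone, makes no Type I error claim.

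**Stronger readings that a reader might infer:**
- *That FDR causes the 7-10% all-null rate.* It does not. Ungated fallback gives almost the same figures, so this is a gating problem.
- *That the protocol's method is unworkable.* It is incomplete. It names a valid procedure and defers only the levels. A fixed sequence headed by the primary could even be read as implying a gate, but the text does not say so.
- *That the protocol states two contradictory testing orders.* Its analysis lists (synopsis and Section 8.4.3.2) open with relapse: "Percent of patients who relapse during the Extended Treatment Period will be compared between 14-day complete responders receiving vigabatrin + CBD". Section 8.1.2 ends with it: "For patients with a complete response during the Initial Treatment Period who continue: percent of patients who relapse during the Extended Treatment Period". But the analysis lists repeat relapse at their end, and no list is called a testing order. The supportable point is that no order is stated.

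**Conclusion.** Wrong as written, and it should be fixed. The SAP synopsis attributes to FDR an error control that it lacks, and both SAP statements conflict with the protocol's fixed sequence with fallback, whose order and levels the SAP never supplies.

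The size is modest: about 5-9% for the SAP's eight hypotheses (Benjamini-Hochberg, half null, design-size effects, correlation 0.7 to 0), up to about 12% with very large effects, and at or below 5% in other configurations. The unstated gate is a second, separate defect, worth about 7-10% trial-wise when all nulls are true, whichever correction is used.

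A reader might infer that the primary conclusion is at risk. It is not: one primary hypothesis is tested once at two-sided 0.05. The consequences are confined to secondary claims, so this falls short of a defect that must be fixed before the trial can be interpreted.

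**What to change.** Before database lock:

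1. In the SAP synopsis and Section 10.5, replace FDR with the protocol's fixed sequence with fallback.
2. State that the secondaries are tested only if the primary is significant at two-sided 0.05.
3. List the secondary hypotheses in a stated order, with fallback weights summing to 0.05 and the carry-forward rule. Give relapse rate and time to relapse separate places, or label one as supportive. The sponsor must choose the order, since no section states one.
4. In Protocol 8.4.3, clarify that 0.05 for all inferential tests is not a per-test level for the secondaries.
5. Build the list from the current protocol. The two partial-to-complete-response hypotheses in SAP 10.3.2 do not match Protocol 3.1.2 and 3.1.3, where only Complete Responders continue and partial responders are offered an open-label study. The protocol still mentions EEG confirmation of complete resolution in the Extended Treatment Period (Schedule of Events video-EEG footnote, Sections 6.1 and 8.4.3). These passages must be reconciled at the same time.

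**Cost.** No new data are needed, but power per secondary falls. As an illustration only, suppose every secondary had the primary's design effect (shift 2.6-2.8). Average power would fall from about 67-77% with ungated Benjamini-Hochberg to about 40-60% with gated, equally weighted fallback over five or six tests. The gate alone accounts for part of this (gated Benjamini-Hochberg: 51-69%). These figures do not apply to relapse, which is tested only among complete responders: about 0.60×130 = 78 against 0.40×60 = 24 at the protocol's design rates. Unequal weights can protect the endpoints the sponsor values most. If the primary fails, no secondary claim is possible.

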### Primary Efficacy Analysis

- Percent of patients with resolution of both infantile spasms and hypsarrhythmia or a pattern of epileptic encephalopathy at Day 14 (complete response) will be compared between Vigabatrin plus Placebo and Vigabatrin plus CBD 40 mg/kg/day groups using Fisher's exact test.

### Secondary Efficacy Analyses

- Percent of patients with resolution of infantile spasms at Day 14 will be compared between treatment groups using Fisher's exact test.
- Percent of patients with resolution of hypsarrhythmia or a pattern of epileptic encephalopathy at Day 14 will be compared between treatment groups using Fisher's exact test.
- Investigator impression of efficacy and tolerability of study drug (Clinical Global Impression – Global Improvement (CGI-I)) will be compared between treatment groups using a t-test.

- Percent reduction in spasm-free days between the Initial Treatment Period (Days 1 to 14) and Screening Period (Days -14 to -1) will be compared between treatment groups using ANCOVA with the baseline score as a covariate.
- Percent of patients who relapse during the Extended Treatment Period will be compared between 14-day Vigabatrin + CBD responders and 14-day Vigabatrin + placebo responders using Fisher's exact test. Time to relapse will be calculated with Kaplan-Meier curves and compared using a log-rank test.
- Percent of patients with partial response at Day 14 who achieve complete response during the Extended Treatment Period will be compared using Fisher's exact test. Time to complete response will be calculated with Kaplan-Meier curves and compared using a log-rank test.

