7.1. Screening Period (Visit 1)

Potential study patients will be examined before the start of the study to determine their eligibility for participation. Prior to performing any study related procedures or assessments, the Investigator will ensure that the patient's legal representative (parent[s]/caregiver[s]) provides written informed consent. Patients and their parent(s)/caregiver(s) will receive a copy of the ICF for review and must provide fully informed consent prior to study participation.

The following screening procedures and assessments are intended to be performed during Visit 1, but the patient may return to complete activities, which must be performed within 14 days of the start of the Initial Treatment Period for all patients.

- Obtain written informed consent.
- Review of inclusion and exclusion criteria (see [Sections 3.2.1](#) and [3.2.2](#)).
- Record demographic data.
- Record recent and concomitant medication and procedure history including vitamins, herbal preparations, blood products, and over-the-counter drugs. All medications taken ≤ 30 days of the Screening Visit must be documented in the concomitant medications section of the CRF.
- Record all prior and current anti-epileptic therapies (AETs, including drugs, ketogenic diet, vagal stimulators etc.)
- Record medical and surgical history.
- Record the types of seizures and the frequency of infantile spasms occurring ≤ 28 days of the Screening Visit based on parent/caregiver recollection.
- Record vital signs (seated or supine blood pressure [depending on patient age and ability], pulse rate, respiratory rate, and temperature measurements).
- Draw blood samples for hematology and chemistry.
 - o [Section 7.4](#) details the volume of samples to be drawn based on patient age.
- Perform a complete physical examination (see [Section 6.2.2](#)), including height, weight, and head circumference.
- Perform a complete neurological examination (see [Section 6.2.3](#)).
- Perform a minimum of 9-hr video-EEG that includes a full sleep-wake cycle.
- Completion of investigator CGI-S.
- Provide daily seizure diary to capture seizure activity (infantile spasms only) between visit 1 and visit 2, and train the caregiver to recognize and capture the infantile spasms.

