8.4.3.2. Secondary Efficacy Analyses

- Percent of patients who relapse during the Extended Treatment Period will be compared between 14-day vigabatrin + CBD responders and 14-day vigabatrin +

placebo responders using a chi-square test. Time to relapse will be described with Kaplan-Meier curves and treatment groups compared using a log-rank test.

- Percent of patients with complete resolution of infantile spasms at Day 15 will be compared between treatment groups using a chi-square test.
- Percent of patients with complete resolution of hypsarrhythmia at Day 15 using a chi-square test.
- Investigator impression of efficacy and tolerability of study drug (Clinical Global Impression – Global Improvement [CGI-I]) will be compared between treatment groups using ANCOVA with baseline CGI-S as a covariate.
- Percent reduction in spasm-free days between the Initial Treatment Period and Screening Period will be compared between treatment groups using ANCOVA with the baseline score as a covariate.

Secondary efficacy analyses for patients with a complete response during the Initial Treatment Period who continue to the Extended Treatment Period:

- Percent of patients who relapse during the Extended Treatment Period confirmed by video EEG following parent report of relapse.
- Time to relapse.

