### 10.3.2. Secondary Efficacy Endpoints

Secondary efficacy endpoints:

- Percent of patients with absence of infantile spasms as assessed by 24-hour video-EEG from Day 13 to Day 14 (partial response).

*Null hypothesis: There is no difference in the percent of patients with absence of infantile spasms between treatment groups.*

*Alternative hypothesis: Treatment groups have significantly different percentage of patients with absence of infantile spasms.*

- Percent of patients with absence of hypsarrhythmia or pattern of epileptic encephalopathy as assessed by 24-hour video-EEG from Day 13 to Day 14 (partial response).

*Null hypothesis: There is no difference in the percent of patients with hypsarrhythmia or pattern of epileptic encephalopathy at Baseline but absence of hypsarrhythmia or pattern of epileptic encephalopathy at Day 13 to Day 14 between treatment groups.*

*Alternative hypothesis: Treatment groups have significantly different percent of patients with hypsarrhythmia at Baseline but absence of hypsarrhythmia at Day 14 to Day 15.*

- Investigator impression of efficacy and tolerability of study drug (CGI-I) at End of Study/Early Withdrawal (Visit 5).

*Null hypothesis: There is no difference in the mean CGI-I score between treatment groups.*

*Alternative hypothesis: Treatment groups have significantly different mean CGI-I score.*

- Percent reduction in spasm-free days between the Initial Treatment Period (Days 1 to 14) and Screening Period (Days -14 to -1), as determined by the seizure diary entries.

*Null hypothesis: There is no difference in the percent reduction in spasm-free days between treatment groups.*

*Alternative hypothesis: Treatment groups have significantly different percent reduction in spasm-free days.*

- For patients with a complete response during the Initial Treatment Period who continue: percent of patients who relapse during the Extended Treatment Period confirmed by video-EEG following parent report of relapse, and time to relapse.

1. *Null hypothesis: there is no difference in the relapse rate between Vigabatrin + Placebo Responders and Vigabatrin + CBD Responders.*  
*Alternative Hypothesis: The relapse rate is different Vigabatrin + Placebo Responders and Vigabatrin + CBD Responders.*
  2. *Null hypothesis: there is no difference in time to relapse between Vigabatrin + Placebo Responders and Vigabatrin + CBD Responders.*  

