### **10.7. Analysis of the Secondary Efficacy Endpoints**

#### **10.7.1. Secondary Efficacy Endpoints**

The secondary efficacy endpoints in this study are:

- Percent of patients with resolution of infantile spasms as assessed by 24-hour video-EEG from Day 13 to Day 14 (partial response).
- Percent of patients with resolution of hypsarrhythmia or pattern of epileptic encephalopathy as assessed by 24-hour video-EEG from Day 13 to Day 14 (partial response).
- Investigator impression of efficacy and tolerability of study drug (CGI-I) at Visit 5 (End of Study) or Early Withdrawal.
- Percent reduction in spasm-free days between the Initial Treatment Period (Days 1 to 14) and Screening Period (Days -14 to -1), as determined by the seizure diary entries.
- For patients with a complete response during the Initial Treatment Period who continue: percent of patients who relapse during the Extended Treatment Period confirmed by video-EEG following parent report of relapse, and time to relapse.
- For patients with partial response during the Initial Treatment Period who continue: percent of patients who achieve complete response during the Extended Treatment Period, confirmed by video-EEG following parent report, and time to complete response.

Percentage of patients with partial response will be compared for each endpoint between treatment groups using Fisher's exact test.

Parent impression of efficacy and tolerability as measured by Clinical Global Impression – Global Improvement Scale (CGI-I) will be summarized by visit and status of response (complete/partial and no response). Appropriate summary statistics will be displayed and the CGI-I will also be analyzed as a continuous scale:

- 1 = Very much improved
- 2 = Much improved
- 3 = Minimally improved
- 4 = No change

5 = Minimally worse

6 = Much worse

7 = Very much worse

Percent reduction in spasm-free days, will be calculated for each treatment group. Treatment groups will be compared using ANCOVA with baseline number of spasm-free days as a covariate.

Percent of Responders who relapse and Partial Responders who achieve complete response during the Extended Treatment Period will be compared between treatment groups using Fisher's exact test. Time to relapse and time to complete response will be visualized using Kaplan-Meier curves and compared with log-rank tests.

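### The SAP tests CGI-I with an unadjusted t-test and never mentions CGI-S, while the protocol specifies ANCOVA on the baseline CGI-S it collects at screening

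*SAP*

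**What the plan says.** **SAP.** The CGI-I bullet in the SAP synopsis says that CGI-I "will be compared between treatment groups using a t-test". The general rule for continuous endpoints, slightly earlier in that synopsis, is looser: "a t-test or ANCOVA will be used to compare treatment to placebo group". In the body, Section 10.3.2 states the null hypothesis as "There is no difference in the mean CGI-I score between treatment groups", and Section 10.7.1 says that "the CGI-I will also be analyzed as a continuous scale" without naming a test or a covariate. CGI-S is not mentioned in the abbreviations, the screening visit (4.1), the efficacy assessments (5.2), the baseline efficacy evaluations (9.7), the CGI-I analysis (10.7.1) or the list of tables (14.2).

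**Protocol.** Section 8.4.3.2 says that CGI-I "will be compared between treatment groups using ANCOVA with baseline CGI-S as a covariate", and the synopsis bullet for CGI-I says the same. Section 8.4.3 makes ANCOVA the method for continuous endpoints, with an ANCOVA on ranks or another non-parametric method if normality fails. The baseline value exists: Section 7.1 lists "Completion of investigator CGI-S" among the screening procedures, and Section 6.1 and the schedule of events agree. One line points the other way. For continuous endpoints in general, the protocol synopsis says "a t-test will be used to compare treatment to placebo group".

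**The concern.** The two documents name different tests for the same endpoint, and the two tests can give different p-values. CGI-I is a tested secondary endpoint inside a multiplicity procedure in both documents: a fixed sequence with fallback in the protocol, and a false discovery rate correction at q = 0.05 in the SAP. Under either procedure its p-value can affect what is concluded for other endpoints. While both methods stand, the choice could be made after the data are seen.

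The protocol leaves detailed methods to the SAP (Section 8), so the SAP's wording is what a programmer would follow. As written, the SAP gives no instruction to use CGI-S, or even to tabulate it. If CGI-S predicts CGI-I, the t-test gives up precision that the trial has already collected the data to gain.

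**Working it through.** **1. The texts side by side**

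| Place | Method for CGI-I | CGI-S used? |
|---|---|---|
| Protocol synopsis, CGI-I bullet | ANCOVA | yes |
| Protocol 8.4.3.2 | ANCOVA | yes |
| Protocol 8.4.3, general rule | ANCOVA, rank-based or other non-parametric if non-normal | baseline value |
| Protocol synopsis, general rule | t-test | no |
| SAP synopsis, general rule | t-test or ANCOVA | not named |
| SAP synopsis, CGI-I bullet | t-test | no |
| SAP 10.7.1 | continuous scale, no test named | no |

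Within the protocol, the specific bullet and both body sections agree on ANCOVA. Within the SAP, the general rule leaves the choice open and the specific bullet then chooses the t-test.

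SAP Section 10.2 does not settle it either. It brings in covariates only when a potentially important baseline imbalance is seen, which depends on the data, and it does not name CGI-S.

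**2. Size of the possible precision loss**

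There is no planned figure to reproduce. Neither document gives an effect size, standard deviation or power for CGI-I, or its correlation r with CGI-S. The calculation below is therefore an illustration over assumed values of r.

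Inputs: 130 and 60 patients (Protocol 8.2); two-sided alpha 0.05 with no multiplicity adjustment (assumed for scale); standardised difference d = 0.4 (assumed).

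- Residual variance under ANCOVA = (1 − r²) × unadjusted variance.
- Standard error in SD units = √(1/130 + 1/60) × √(1 − r²) = 0.1561 × √(1 − r²).
- Power ≈ Φ(d / SE − 1.960).

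At r = 0: 0.4 / 0.1561 = 2.563; 2.563 − 1.960 = 0.603; Φ(0.603) = 72.7%.

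| r | Variance lost by the t-test (r²) | Power with ANCOVA |
|---|---|---|
| 0 | 0% | 72.7% |
| 0.1 | 1% | 73.1% |
| 0.2 | 4% | 74.4% |
| 0.3 | 9% | 76.6% |
| 0.5 | 25% | 84.1% |

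The r = 0 row is also the power of the t-test at any r, since the t-test ignores the covariate.

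**3. The same check on the SAP's allocation**

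With 120 and 60 patients (SAP 3.3), fix the effect so that the t-test has 80% power: d = (1.960 + 0.842) × √(1/120 + 1/60) = 0.443. ANCOVA then has 80.4% power at r = 0.1, 83.6% at 0.3 and 89.9% at 0.5. To match ANCOVA on 180 patients, the t-test would need 180 / (1 − r²) patients: about 182, 198 and 240. The pattern does not depend on which allocation is used.

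**The case against.** **The gain may be close to nothing.** This stands. CGI-I is itself a rating of change from the patient's own starting state, so its correlation with baseline severity could be small. A reader might infer that the t-test throws away a known and material amount of information, for example the 9% to 25% that goes with r of 0.3 to 0.5. The documents do not support that. They give no r, and the honest range starts at zero.

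**The power figures ignore multiplicity.** This also stands. They are computed at 0.05, whereas the level CGI-I would face depends on the multiplicity procedure, on which the documents differ. They show scale only.

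**Validity is not threatened.** Correct. A reader might infer that the unadjusted test is wrong or biased. Under randomisation, omitting a baseline covariate does not bias a comparison of means. The primary endpoint is not touched.

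**The SAP may simply be out of date.** This is likely. SAP Section 1 says it is based on protocol V2.0 of 30 October 2017. The protocol under review cites posters from December 2017, so its text is later. A reader might infer that the SAP's authors chose to drop the covariate. That cannot be shown, because V2.0 is not available and may not have included CGI-S. This explains the gap but does not close it: the SAP says it may evolve with protocol amendments and must be final before database lock.

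**The protocol's own inconsistency is minor.** Agreed. Its general t-test line is outweighed by the specific CGI-I bullet and by Sections 8.4.3 and 8.4.3.2; aligning it is tidying.

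**Conclusion.** The conflict is established from the text alone and needs no assumption: the SAP names an unadjusted t-test for CGI-I, the protocol names ANCOVA with baseline CGI-S, and the SAP omits a covariate collected at screening. No other SAP provision resolves it. The point would remain even if r were zero, because a secondary endpoint under multiplicity control should have one prespecified test.

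The precision loss is possible but of unknown size. It equals r² of the variance: nil at r = 0, 1% at 0.1, 9% at 0.3 and 25% at 0.5. In the d = 0.4 illustration, power rises from 72.7% by between nothing and about 11 points (84.1 − 72.7 = 11.4) as r goes from 0 to 0.5. Those powers rest on the assumed d, the assumed r, the normal approximation and an unadjusted 0.05. The point concerns one secondary endpoint, and bears on prespecification and efficiency.

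**What to change.** Before unblinding:

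- In the SAP synopsis, replace the t-test in the CGI-I bullet with ANCOVA on CGI-I, with treatment and baseline CGI-S as terms.
- Add the same method to SAP Section 10.7.1. That section names no CGI-I test at present, so there is nothing there to replace.
- Carry over the fallback in Protocol 8.4.3 (rank-ANCOVA or another non-parametric method), naming the one to be used. It matters for a seven-point ordinal scale.
- Add CGI-S to SAP Section 5.2 and to the baseline summaries. Say what happens to a patient with no CGI-S, since missing values are not imputed and ANCOVA would drop that patient.
- In the protocol synopsis, bring the general t-test line for continuous endpoints into agreement with Section 8.4.3.

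The cost is wording in the two documents. CGI-S is already collected, so no visit, assessment or patient is added.
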